#### B. ONLY ONE VACCINE ARRIVES AT EACH CENTRE PRIOR TO REGULATORY APPROVAL:

This scenario is the one most likely to occur. It will be implemented if all regulatory approval is in place, AND only one of the two trial vaccines is available in each centre, AND the second vaccine will not arrive within five days of arrival of the first vaccine. Subjects who meet the study admission criteria will be enrolled into the study and will be assigned a **5 digit subject number**:

As before the statistician would generate three 'randomisation' lists for each centre, with a list for each age band.

As before, the first digit identifies the study site (1 for Leicester; 2 for Nottingham; 3 for Sheffield);  
As before, the second digit reflects the age of the subjects on Day 0 (1 for 18-44; 5 for 45-64; and 9 for 65 years and older);

As before the next three digits identify the subject within the site.

HOWEVER, the distribution of the numbers will be randomised, with the first 60 numbers corresponding to the first vaccine to arrive (Vaccine 1), and the second 60 numbers corresponding to the second vaccine (Vaccine 2).

As an example, the first person to be vaccinated in Leicester could have the number 10054, i.e., with '1' corresponding to Leicester, '0' reflecting that he/she is aged 18-44 years, and '054' being the volunteer's unique trial number.

Each centre will continue recruiting volunteers within an age band until the tally for the centres reaches a total of 60 subjects for that age band for Vaccine 1. The same process will then be carried out with Vaccine 2, when it arrives.

Depending on the interval between arrival of GSK and Baxter vaccines, we will endeavour to ship sera from some volunteers who received Vaccine 2 in the first tranche of sera that was sent for analysis. The laboratory staff will not know when Vaccine 2 arrived and was first given, so will not know whether sera were collected from recipients of GSK or Baxter vaccine.

Vaccinees will not be told which vaccine they receive. They will be instructed to look away, both during preparation and administration of the vaccine. It is essential that volunteers do not see the syringe that is used or whether the vaccine is translucent or cloudy.

As before, only one study nurse/doctor will be responsible for vaccine administration in each centre. This study nurse/doctor will be un-blinded with respect to the type of vaccine administered; he/she will play no other role in the study.

The 'Vaccine' study nurse/doctor will record the volunteer's trial number, together with the vaccine that was administered (the adhesive label in the envelope) in the 'Vaccine Log'.

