### **A. BOTH VACCINES ARRIVE AT EACH CENTRE PRIOR TO REGULATORY APPROVAL**

We will use a block randomisation scheme to ensure that balance between vaccines is maintained and all volunteers are randomly allocated to groups. Subjects who meet the study admission criteria will be enrolled into the study and will be assigned a **5 digit subject number**:

The first digit identifies the study site (1 for Leicester; 2 for Nottingham; 3 for Sheffield).

The second digit reflects the age of the subjects on Day 0 (1 for 18-44; 5 for 45-64; and 9 for 65 years and older).

The following three digits identify the subject within the site and will be assigned sequentially, starting with 001 corresponding to the first subject enrolled within each age band.

Thus each centre will have three randomisation lists, each list corresponding to each age band.

Each centre will continue recruiting volunteers within an age band until the tally for the centres reaches a total of 120 subjects for that age band.

Volunteers in each age band will be randomised by a computer generated randomization code (1:1 proportions in block size(s) that will be determined by the statistician to ensure balance across groups). The randomisation code for each age band will be stored in individual, sequentially-numbered envelopes, specific for each centre, and will be opened by the nurse with responsibility for vaccine administration. The type of vaccine for administration will be printed on an adhesive label. The label will be peeled from its backing and entered into an appropriate space in the 'Vaccine Log', ensuring that the instruction and vaccine that is administered actually agree (See below).

Only one study nurse/doctor will be responsible for vaccine administration in each centre. This study nurse/doctor will be un-blinded with respect to the type of vaccine administered; he/she will play no

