### 9.2.5.3 Exploratory analyses

The possible effect of previous seasonal influenza vaccination, age, presence of detectable levels of antibody before vaccination, as well as vaccine type – and any interactions will be explored using (generalised) linear models.

If one vaccine is available significantly before the other, then the trial will adopt a sequential allocation procedure switching to randomisation when the second one becomes available. If such a situation arises then the comparisons outlined in 9.2.5.1 will be non-randomised ones and potentially subject to bias (for example due to temporal effects). In this situation the use of date (time) of vaccination will also be used as an explanatory covariate in (generalised) linear models in order to explore the potential impact of this on the trial outcomes.

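### Section 7.4 B fills a separate pooled tally for each vaccine, so the two vaccines can end up with different centre mixes, an avoidable bias in the head-to-head comparisons

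*Protocol*

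**What the plan says.** Section 7.4 gives two allocation procedures.

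- **Scenario A, both vaccines on site.** "Thus each centre will have three randomisation lists, each list corresponding to each age band". Within each list allocation is in "1:1 proportions in block size(s) that will be determined by the statistician to ensure balance across groups". Recruitment runs "until the tally for the centres reaches a total of 120 subjects for that age band", so the centres compete for places, but for both vaccines together.
- **Scenario B, one vaccine first.** The protocol says of it: "This scenario is the one most likely to occur". Each centre again has a list per age band, but the list is a run of 60 Vaccine 1 numbers followed by a run of 60 Vaccine 2 numbers. For Vaccine 1 the rule is: "Each centre will continue recruiting volunteers within an age band until the tally for the centres reaches a total of 60 subjects". Then: "The same process will then be carried out with Vaccine 2, when it arrives". No centre has a quota for either vaccine.

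Section 9.2.5.3 accepts that comparisons under sequential allocation are not randomised, and gives time effects as its example of bias. Its remedy is: "In this situation the use of date (time) of vaccination will also be used as an explanatory covariate in (generalised) linear models". Centre is not named there. Section 9.2.5.1 refers only to baseline covariates in general.

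The two sections also disagree. In 9.2.5.3 allocation changes to randomisation once the second vaccine is available, whereas 7.4 B gives all of the second 60 to Vaccine 2.

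**The concern.** Two separate first-come tallies allow any split of centres for either vaccine, from 60/0/0 to 0/0/60. The documents offer ways in which the split could move between the two periods. Section 6.7.1 approaches frontline staff first, with GP patients and advertising as possible further sources, so a centre that supplied much of Vaccine 1 may have used up its readiest volunteers. Section 7.4 B does not require Vaccine 2 to reach all centres on the same day, and the first to receive it could take most of the places.

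Centres may differ in the people they recruit, in local H1N1 exposure and in the on-site examination of injection sites; each also has its own single vaccinator. If the mix differs by vaccine, these differences enter the vaccine contrast. The comparisons at stake are those of titres and response rates in 9.2.5.1, which are made only if both vaccines meet the criteria, and those of reactions in 9.2.6, which carry no such condition.

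**Working it through.** **Counts.** 2 vaccines x 60 = 120 per age band, and 120 x 3 age bands = 360. This reproduces the total in the synopsis table of subject numbers. No stated figure is in dispute; the issue is how each 60 is filled.

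**Formula.** With no true vaccine difference, the spurious difference is the sum over centres of (share of one vaccine minus share of the other) x centre level. For titres this is computed on the log scale and then exponentiated.

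**Assumed inputs.** The documents give no centre mix and no centre gradient. Take 30/20/10 for Vaccine 1 and 10/20/30 for Vaccine 2 in one age band. The share differences are -1/3, 0 and +1/3. Let the centre level rise linearly, with scores 0, 0.5 and 1 times the full gradient. The net shift is then 1/3 of the gradient.

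| Assumed gradient, end centre to end centre | Calculation | Spurious effect |
|---|---|---|
| GMT 1.5-fold | exp(ln 1.5 / 3) | ratio 1.14 |
| GMT 2-fold | exp(ln 2 / 3) | ratio 1.26 |
| Rate, 15 points | 15 / 3 | 5 points |

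**Range.**
- Half the shift (30/20/10 v 20/20/20): ratios exp(ln 1.5 / 6) = 1.07 and exp(ln 2 / 6) = 1.12, and 15 / 6 = 2.5 points.
- A stronger reversal (40/15/5 v 5/15/40) with rates 20 points apart around 80%: 35/60 x 20 = 11.7 points. With 60 per vaccine and a two-sided 5% test, the chance of a false positive is about 36%. For comparison, section 9.2.1 names a difference of 10% to 20% as its target.
- Equal centre mixes: zero, whatever the centre levels.

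**Scenario A for comparison.** Only incomplete blocks remain. With an assumed block size of 4, a centre can be out by at most 2, which gives 2/60 x 20 = 0.7 points when the end centres are 20 points apart.

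**Can chance alone produce the illustrated shift?** If the centres recruit at equal and stable rates, the scores 0, 0.5 and 1 have variance 1/6. The SD of the difference in mean score between the vaccines is sqrt(2 x (1/6) / 60) = 0.075. The illustrated shift of 1/3 is about 4.5 of these SDs. A shift of that size therefore needs a real change in relative recruitment between the periods.

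**Cost of adjusting for centre.** At 30/20/10 v 10/20/30 each centre has 40 subjects, and the Vaccine 1 proportions are 0.75, 0.50 and 0.25. Regressing vaccine on centre gives R-squared = ((0.25² + 0 + 0.25²) / 3) / 0.25 = 1/6. The variance inflation is 1 / (1 - 1/6) = 1.2, so the SE widens by sqrt(1.2), about 10%.

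**The case against.** The strongest reply is that with stable centre recruitment rates the two runs have the same expected mix. That stands. A reader might infer that the centre mix would go wrong even if nothing changed over time. The documents do not support this: beyond chance, a shift in recruitment between the periods is needed. What remains separate from time is the mechanism. Given such a shift, the bias arises even if titres and reactions themselves do not change with date.

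A reader might also infer that adjustment could not repair the comparison. At the illustrated mix it can, for about 10% in SE. It fails only when a centre gives almost entirely one vaccine, which 7.4 B permits but nothing in the protocol predicts. Centre is recoverable from the first digit of the subject number, and an analysis plan not shown could name it. That would help the analysis but would not change the allocation rule.

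Further points stand. The primary objective judges each vaccine against fixed thresholds and does not rest on the contrast. HI and MN assays are run at one laboratory, serum handling follows one procedure, and daily symptoms are self-scored on a common diary card, so assay and handling are weak routes for a centre effect. Scenario B has centre lists too; what protects scenario A is the blocking inside them.

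Finally, pooled tallies are fast. Section 6.2 expects about two weeks of enrolment, and section 9.2.7 wants results quickly. A rigid cap could lengthen Vaccine 2 enrolment and widen the calendar gap that 9.2.5.3 already concedes. This argues for a target that is released early, not for having no target.

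**Conclusion.** The point holds in a limited form. Section 7.4 B lets centre mix differ by vaccine in the scenario the protocol expects, and the added analysis in 9.2.5.3 names only date. This adds an avoidable source of bias to the between-vaccine comparisons. It does not undermine the single-vaccine licensing criteria in the same way, and the documents do not show that the mixes will differ.

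The spurious ratios of 1.14 and 1.26 and the 5-point difference rest on an assumed exact reversal of centre shares and on assumed centre gradients; half the shift roughly halves them. Late delivery makes the calendar-time bias hard to escape, but centre mix remains under the sponsor's control. The importance is modest, and the case for acting is that the change is cheap.

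**What to change.** 1. Reconcile 7.4 B with 9.2.5.3 on allocation after the second vaccine arrives: all remaining places to Vaccine 2, or a switch to randomisation. The form of any centre target depends on the answer. Even with a switch, subjects vaccinated before it could have a different centre mix.
2. Where allocation stays sequential, state in 7.4 B that each centre's Vaccine 2 target in each age band equals the number it gave Vaccine 1 in that band. Release unfilled places to all centres on a stated early date, so that enrolment is not prolonged.
3. In 9.2.5.3, name centre beside date of vaccination as a covariate.

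The cost is a few sentences and a tally by centre shared between sites. The last Vaccine 2 places may fill a few days later, and adjustment widens the SE slightly (about 10% at the illustrated mix). Places released after the date can bring back some imbalance, which the centre term then has to absorb.

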**The H1N1v vaccines purchased by the Government** The UK Departments of Health have purchased pandemic vaccines from Baxter Healthcare and GlaxoSmithKline. The Baxter vaccine (trade name, Celvapan) is a plain (i.e., non-adjuvanted), whole virus, vero-cell-grown, influenza A (H1N1)v pandemic formulation, containing 7.5µg HA per 0.5mL dose. The GlaxoSmithKline vaccine (trade name, Pandemrix) is an AS03-adjuvanted, split-product, egg-grown, influenza A (H1N1)v formulation, containing 3.75µg HA and oil-in-water AS03 adjuvant composed of squalene, DL- $\alpha$ -tocopherol and polysorbate 80. The expectation is that the initial limited supplies of both vaccines will be prioritised for those deemed to a greatest risk, but eventually everyone will have access to either vaccine. To ensure that protection is provided as rapidly as possible, it is imperative that vaccine is used efficiently.

**Conclusions** The available evidence indicates that whole virus vaccines, and split and subunit vaccines that contain oil-in-water adjuvant, are more immunogenic for avian H5, H7, and H9 HAs, and A/New Jersey/76 (H5N1) and A/USSR/77 (H1N1) than split and surface antigen vaccines without adjuvant. They also offer the potential for broadened antibody responses that could be critical in the event of antigenic drift during the course of the pandemic. Vaccine is likely to be in short supply (vaccine production takes time and is subject to various rate-limiting factors) and demand will be high worldwide. The available antigen will therefore need to be given optimally with consideration being given to the logistics of vaccine administration, immune responses, and the frequency and nature of adverse clinical reactions.

There have been no head-to-head comparisons of avian vaccines manufactured by Baxter Healthcare and GSK. Due to variability of serological assays, there are uncertainties as to whether

one preparation offers advantages over the other in terms of dose sparing in ‘older’ people, and significantly more ‘seroconversions’ in the young.

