**9.2.4 Analysis of immunogenicity criteria**

Blood samples for immunogenicity assays will be collected on Days 0 (prevaccination), 7, 14, 21, 28, 35, 42, and 180.

Antibody response will be evaluated by haemagglutination inhibition (HI), neutralization (MN), and possibly single-radial haemolysis (SRH) in all subjects.

HI and/or MN antibody titres need to be assessed rapidly and so will be analysed in three tranches:

- 1st tranche of sera measuring antibodies before and after 1st injection: Days 0, 7, 14, and 21
- 2nd tranche of sera measuring antibodies before and after 2nd injection: Days 21, 28, 35, and 42.
- 3rd tranche of sera measuring persistence of antibodies: Days 0, 42 and 180.

HI and MN assays will be performed at the Health Protection Agency Centre for Infections, Enteric, Respiratory & Neurological Virus Laboratory, London, UK. SRH tests may be done at the National Institute for Biological Standards and Control. Antibody titrations will be done in duplicate. Pre- and post-vaccination samples from each person will be titrated simultaneously, as specified in the CHMP guidance. The titre assigned will be the geometric mean of two independent determinations.

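### Under sequential allocation the two vaccines' sera may largely be assayed in different runs, so a run-to-run shift would be confounded with vaccine in the titre and threshold comparisons

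*Protocol*

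**What the plan says.** Protocol Section 7.4 B applies when one vaccine is on site and "the second vaccine will not arrive within five days of arrival of the first vaccine". No upper limit on the gap is given. Of this case it says: "This scenario is the one most likely to occur". Numbers are allotted "with the first 60 numbers corresponding to the first vaccine to arrive (Vaccine 1), and the second 60 numbers corresponding to the second vaccine", separately in each age band. Depending on the gap, "we will endeavour to ship sera from some volunteers who received Vaccine 2 in the first tranche of sera that was sent for analysis". The sentence that follows concerns keeping the laboratory blind.

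Section 9.2.4: "HI and/or MN antibody titres need to be assessed rapidly and so will be analysed in three tranches". Tranche 1 covers Days 0, 7, 14 and 21. Tranche 2 follows the second "injection: Days 21, 28, 35, and 42". Tranche 3 is the "tranche of sera measuring persistence of antibodies: Days 0, 42 and 180". Tranches are defined by study day; their make-up by vaccine is not stated. Each person's pre- and post-vaccination sera are to be titrated at the same time, in duplicate, with HI and MN in one laboratory.

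Section 9.2.5.1 compares the vaccines, if both meet all three criteria, on GMT, geometric mean ratio, seroprotection and seroconversion 21 days after each dose. Section 9.2.5.3 concedes that under sequential allocation these comparisons are non-randomised and open to temporal bias, and adds vaccination date as an exploratory covariate.

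The Conclusions of Section 4.0 give the reason for a head-to-head trial: "Due to variability of serological assays, there are uncertainties as to whether" one product has advantages over the other.

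**The concern.** A head-to-head trial removes assay differences only if both products meet the same assay conditions. Here sera are to be read quickly and Vaccine 1 is given first, so Vaccine 1 sera will tend to be titrated earlier. If the laboratory's readings move between the earlier and later runs, the movement lands mainly on one vaccine and looks like a vaccine effect. It changes absolute titres and the share of subjects reaching a fixed cut-off. Analysis cannot restore a balance that was lost at the bench. At stake is a declared difference in GMT or seroprotection that is partly or wholly an assay artefact.

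**Working it through.** **Which outcomes are exposed.** Suppose a run multiplies every titre by a factor f.
- GMT is multiplied by f, so it is exposed.
- Seroprotection (HI ≥40) has a fixed cut-off, so it is exposed.
- Seroconversion from <10 to ≥40 has the same cut-off, so it is exposed.
- Geometric mean ratio and fourfold rise: f cancels where both sera of a person are in the same run and above the detection limit. Tranches 1 and 3 contain Day 0. Tranche 2 does not, so a Day 42/Day 0 ratio built from tranches 1 and 2 is not clearly protected.

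**How much overlap is possible.** Section 6.2 expects about 2 weeks of enrolment. Assume 14 days of even enrolment for each vaccine. The last Vaccine 1 subject then reaches Day 21 on calendar day 14 + 21 = 35. If Vaccine 2 starts on arrival, 7 days after Vaccine 1, the share of its subjects with Day 21 sera by then is (14 − 7)/14 = 50%. With a 14-day gap, or if Vaccine 2 starts only once the Vaccine 1 quota is full, the share is 0 unless the tranche is held. The same holds for Day 42 at calendar day 14 + 42 = 56. Overlap could therefore be large or nil, and the protocol does not fix it.

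**Vaccination date as covariate.** Under Section 7.4 B the dates for Vaccine 2 follow those for Vaccine 1, so date is nearly aliased with vaccine. It is also not the assay run.

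**The plan's own figures.** 60 × (1 − 0.17) = 49.8, about 50 evaluable per vaccine and age group, which agrees with Section 9.2.1; three age groups give 150 per vaccine. That section states a detectable difference of 10% to 20% at 80% power without a base rate. From a base of 70%, a two-sided 5% test needs 21.8 points at 50 per group and 13.7 at 150 per vaccine.

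**Upper bound for the false-positive rate.** Assumed, because the documents give neither: SD 0.5 log10; shift 1.25-, 1.5- or 2-fold. Also assumed: equal vaccines, complete separation by run, and one constant shift.

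δ = log10(f) / (SD × √(2/n)); rate = Φ(−1.96 + δ) + Φ(−1.96 − δ).

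At n = 50 the standard error is 0.5 × √(2/50) = 0.100. At n = 150 it is 0.5 × √(2/150) = 0.058. For seroprotection starting at 70%, the shifted rate is Φ(0.524 + log10(f)/0.5).

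| Shift | log10(f) | δ, n = 50 | GMT rate, n = 50 | GMT rate, n = 150 | Seroprotection, from 70% |
|---|---|---|---|---|---|
| 1.25 | 0.097 | 0.97 | 16% | 39% | 76.4% |
| 1.5 | 0.176 | 1.76 | 42% | 86% | 81% |
| 2 | 0.301 | 3.01 | 85% | >99% | 87.0% |

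The test on seroprotection is less sensitive: at 50 per group its false-positive rate is 11% for 1.25-fold and 54% for 2-fold. For a 1.5-fold shift at 50 per group, an SD of 0.6 or 0.4 gives a GMT rate of 31% or 60%.

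**Partial overlap.** If a fraction q of Vaccine 2 sera shares the Vaccine 1 runs, δ shrinks to (1 − q)δ. At 50 per group and q = 25%, the GMT rates are 11%, 26% and 62%. At q = 50%, a 1.5-fold shift gives 14%. With runs balanced by vaccine the shift cancels and the rate returns to 5%.

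**The case against.** Run composition by vaccine is stated nowhere, so separation is an inference. The protocol does intend some overlap in tranche 1, and a short gap could make it substantial. Section 9.2.5.3 even speaks of switching to randomisation once the second vaccine is available. That conflicts with Section 7.4 B and must be reconciled, but on that reading separation would be smaller. This stands, and it is why the point is that sera may largely be separated.

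A reader might infer that the protocol's figure of up to 32-fold HI variability applies. It does not: it is a between-laboratory figure, and using one laboratory for HI and MN removes that source. Shift between runs in one laboratory is a separate matter and probably smaller.

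A reader might also take 85% as the trial's error rate. It is a bound under the assumptions shown. Tranche 1 alone is up to 180 × 4 = 720 sera per vaccine; if these span several runs, independent run shifts partly average out and mainly systematic drift remains. Duplicate titration does not help with drift, because it reduces random error only.

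The primary objective is each vaccine against the licensing criteria. The head-to-head is conditional on both passing, its P-values are to be read cautiously, and temporal bias is conceded in general terms. All true, but the concession names no assay run and the covariate offered cannot isolate it.

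Control sera and plate layout may be set out in a laboratory manual or the statistical analysis plan, which are not at hand. The shipment and tranche rules, however, are in the protocol, and they leave the balance to best endeavours.

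**Conclusion.** The concern holds in qualified form. In the scenario that the protocol expects, vaccine may be strongly tied to assay run. The only overlap is conditional, unquantified and limited to tranche 1; none is stated for tranche 2. Between-vaccine comparisons of GMT, HI ≥40 and seroconversion from <10 to ≥40 are exposed. Fold rises are protected where a person's pre- and post-vaccination sera are titrated together. Vaccination date cannot separate run from vaccine.

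The size is unknown, because the documents give no within-laboratory shift and no titre SD. Under the stated bound, modest shifts raise the GMT false-positive rate at 50 per group to between 16% and 85%. A 1.5-fold shift moves seroprotection from 70% to about 81%, some 11 points, which lies within the difference that the trial says it can detect. Partial overlap lowers these figures but does not bring them to 5%.

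The documents do not support saying that the sera will be fully separated, that a false difference is likely, or that this confounding undermines each vaccine's own assessment against the licensing criteria. The point should be settled before the first shipment.

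**What to change.** - In Sections 7.4 B and 9.2.4, require sera of both vaccines to be mixed at random within runs, by age band and with a common control serum, wherever both are available.
- Hold tranche 3 until both vaccines' sera exist, run it mixed, and base the final Day 42 head-to-head on its Day 0 and Day 42 titres.
- Label between-vaccine comparisons of GMT and seroprotection from tranches 1 and 2, including Day 21, as provisional and open to run effects, unless those runs were balanced by vaccine or bridged by the control serum. Seroconversion from <10 to ≥40 deserves the same label.

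Cost: a run-order instruction, a control serum and some analysis wording. The Day 0 and Day 42 titrations in tranche 3 are already planned, so no subject sample is titrated again. The definitive Day 42 comparison waits for tranche 3, at least 180 − 42 = 138 days after the Day 42 visit, and tranche 3 itself waits for the later vaccine. Tranche 3 holds no Day 21 sera, so the Day 21 comparison becomes definitive only if its own runs are balanced or bridged. Interim reports and each vaccine's assessment against the licensing criteria still go out on time.
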